Phone Screen. Interested youth will call into our program line, and will be evaluated by our trained research assistant (RA) over the phone using our established phone screen. Youth referred by other research or community groups (such as the justice departments) will be contacted by an RA to receive more information about participation opportunities and to complete the phone screen if interested. During screening, potential participants will be informed of the general procedures for the study, and if interested, will answer several questions to establish potential eligibility.

For inclusion, youth must : **(1)** be aged 14-19, and complete the entire study before turning 21 **(2)** have not participated in any of the PI's prior or current studies, **(3)** be currently binge drinking (defined as 3+ drinks per drinking occasion for girls, and 4+ drinks per drinking occasion for boys; with a minimum of 1 binge drinking event during the past two months, with enrollment priority going to those who are heavier drinkers, e.g., ≥ 3 binge drinking events in the past month) ([name] et al 2013a), **(4)** have breath alcohol level of 0 before participating in all study components, **(5)** have not used recreational drugs, including prescription medications used without a prescription and/or used in a way counter to the intended dose/use, more than 3 times (total; doesn't have to be more than three uses of a single substance) in the past month (exceptions are marijuana, tobacco, and e-cigarette products, which are permitted due to high comorbidity with alcohol use) **(6)** agree to be contacted to participate for 3-, 6-, and 12-month follow-ups, **(7)** for youth ages ≤ 17 years: informed consent of a parent or legal guardian; and **(8)** all youth: personal informed assent/consent.

With respect to the fMRI component, we have attempted to maintain tight control over factors that may increase error variability and that maximize protection for our participants. Thus, our exclusion criteria are: (1) history of brain injury or neurological diagnoses (including loss of consciousness \geq 2 minutes), (2) currently taking psychotropic medications (e.g., neuroleptics, anticonvulsants), (3) current psychotic disorder, (4) neurodevelopmental disorder, (5) pregnancy (as self-reported or tested immediately prior to scans), (6) fMRI contra-indications (e.g., non-removable metal implants, braces, claustrophobia), and (7) left-handedness.

c) Vulnerable Populations

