participants' future goals and attitudes using the **Future Orientation Scale** (Steinberg et al., 2009), and the **Goal Orientation Scale** (Child Trends). **Counselor Measures** (Feldstein et al., 2012) to gather the counselor's subjective assessment of the MI and BAM interventions. We will administer the **Wechsler Abbreviated Scale of Intelligence** (WASI; Wechsler 1999) Vocabulary and Matrix Reasoning subtests and an fMRI **Theory of Mind** task (cartoon stories) (Sebastian et al., 2012) to evaluate basic cognitive skills. We will query youth's level of agreement with each presented counselor statement ([name] under review), presented in their individualized fMRI paradigm via likert scale immediately after their fMRI session in the **Scanner Exit Questionnaire**. We will assess client sleepiness during the scan with the Karolinska **Sleep Scale** (Akerstedt & Gillberg, 1990). Finally, we will administer the **Working Alliance Inventory** (Tracey & Kokotovic 1989) to all counselors and youth at the end of each session to assess youth and counselor perspectives of therapeutic alliance, along with the **Counselor and You** scale (Aron et al., 1992), client and counselor ratings of the **Most Important In-Session Clinical Moment** (Walsh 2004) and client and counselor ratings of the **Therapist's Level of Empathy and Warmth** (Miller & Moyers, 2013). Following Session 1, the counselor will select the 20 most relevant BAM or MI statements using the **BAM or MI Counselor Statement Selections** worksheet, which allows the NILE fMRI to be catered to individual participants.

Intervention Session 1:

Experimental Condition: Half of the enrolled youth will receive 2 60-minute MI sessions which explicitly target reducing problem drinking. All sessions will be conducted by a postdoctoral fellow or graduate-level counselor and will proceed according to our established adolescent MI manual ([name] et al 2008). The first session is focused on an open-ended exploration of youth's problem drinking behavior. This session is audio-recorded to facilitate the transfer of within-session statements to the fMRI task (see Session 1 MI).

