Sample size was selected to evaluate the primary research questions at a two-tailed alpha of .05 and power of .80. Estimates of effect size were conducted in G*Power 3 (Faul et al 2009, Faul et al 2007). For **Hypothesis 1**, the relationship between MI-consistent therapist statements and brain-based response, in our pilot evaluation, we found that MI-consistent behaviors (as contrasted with non-MI-consistent behaviors) showed a large effect size ($z = 2.27$, $d = 1.31$) within the IFG ([name] et al under review-a). Thus, this effect size requires a sample size of 22 subjects to power Hypothesis 1. In terms of **Hypothesis 2**, that brain activity will correlate with reductions in proximal and distal problem drinking, our pilot study showed significant relationships between MI-consistent therapist behaviors and proximal (1-month) reductions in binge drinking days (right IFG $z = 3.38$, $d = 1.95$; insula $z = 2.238$, $d = 1.29$) ([name] et al under review-a); thus, for this analysis, we would need 22 subjects to detect proximal behavior change. However, because no study to our knowledge has evaluated how BOLD response relates to youths' distal (12-month) behavior change, we suggest a more conservative (medium) effect size of $d = .70$ for this heretofore unexamined relationship. Together, this suggests the need for 68 youth to detect both proximal and distal behavior change for Hypothesis 2. For **Hypothesis 3** we refer to the work of Fritz and MacKinnon (2007) to determine sample size for our mediation hypothesis. For the A path, the relationship between therapist speech and adolescent BOLD response, our pilot evaluation suggests a large effect for MI-consistent therapist behaviors on BOLD activation. For the B path, the relationship between youth brain response and subsequent behavior change (proximal and distal treatment outcomes), we anticipate a medium effect size. For the indirect effect, that is, the effect of therapist speech upon problem drinking outcomes mediated by youth brain response, Fritz and MacKinnon indicate that with a large effect for the A path and a medium effect for the B path, we would need a sample of $N = 204$ to detect a mediated effect for Hypothesis 3 with power of .80 at an *a priori* alpha of .05.

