The Impact of Attrition. In our prior NIAAA R01 with drinking youth (PI [name]), we have an established track-record of retaining ~84% of adolescents at our most distal (12 month) follow-up. Thus, we project losing 16% of the proposed sample, thus requiring **N = 243** youth to account for attrition.

Analysis Plan.

Analyses will be conducted to evaluate (1) the relationship between therapist behavior and youth brain response (BOLD), (2) the relationship of youth brain response (BOLD) to changes in youth problem drinking across proximal (3- and 6-month) and distal (12-month) follow-ups, and (3) the mediational role of BOLD activation on the relationship between therapist behaviors and youth problem drinking outcomes. Measures will be derived from the baseline fMRI scan and behavioral data collected at baseline, 3-, 6- and 12-months.

fMRI preprocessing and single-subject analysis. The first three volumes of each run will be discarded to allow the MR signal to reach steady state. The remaining images in each youth's time series will be motion corrected (Jenkinson, Bannister, Brady, & Smith, 2002) using FSL's MCFLIRT module (FMRIB's Software Library). Images will be spatially smoothed with a 3D Gaussian kernel ($FWHM = 8 \text{ mm}^3$), intensity normalized and temporally filtered with a 50 sec high pass filter FEAT (FMRIB's Easy Analysis Tool) (Smith et al., 2004).

We will utilize a regression approach (GLM - general linear model) to extract regularities with regard to temporal aspects (i.e., time series) of the data. Statistical analysis will be carried out using FILM (FMRIB's Improved Linear Model) with local autocorrelation correction. We will create an explanatory variable (EV) for each trial type (MI-consistent, BAM-consistent, BAM- and MI-inconsistent). For each participant, we will use FILM to obtain a parameter estimate for each EV and create appropriate contrasts. Contrast maps of parameter estimates (PE) for each youth are transformed into a common stereotaxic space using the following 2-step registration prior to the group analyses. Statistical maps will be warped into the common MNI stereotaxic space (Jenkinson et al., 2002) before a random effect group analysis is performed. To do so, (1) the EPI image will be registered to the participant's high resolution T1 weighted image; (2) the T1-weighted high resolution image will be registered to the MNI 152 brain template image; and (3) statistical images

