will be transformed to MNI space using the transformations matrices from step 2. Coordinates will be reported in MNI space. All registration will use FNIRT (FMRIB's Nonlinear Image Registration Tool).

To test **Hypothesis 1**, that MI-consistent therapist behaviors will be associated with greater BOLD response (MFG, IFG, insula) than MI-inconsistent therapist behaviors, we will utilize the same procedure used in our pilot study ([name] et al under review-a). Group-level activations will be evaluated for MI-consistent vs. MI-inconsistent for change talk (CT) and sustain talk (ST) separately across the whole brain and thresholded using a false discovery rate (FDR) set to a false-positive $p < 0.05$. Following our prior work ([name] et al under review-a, [name] et al 2013b), to test **Hypothesis 2a** (from original submission), that BOLD response will be directly associated with proximal (3-, 6-month) and distal (12-month) behavior change (reductions in youth problem drinking), we will utilize an index of youth problem drinking (past month binge drinking days; derived from TLFB + past month alcohol-related problems; derived from RAPI). We will conduct linear regression analyses in FSL with baseline measures of alcohol use behavior and alcohol problems included as regressors to assess correlations between BOLD response and behavior change for youth problem drinking at each follow-up time point. To test **Hypothesis 2b** of the Supplement, that greater BOLD response will be directly associated with proximal (3-, 6-month) and distal (12-month) behavior change (reductions in youth cannabis use), we will utilize an index of youth problem cannabis use (past month cannabis use days; derived from TLFB + past month cannabis related problems; derived from Cannabis Problems Questionnaire). We will conduct linear regression analyses in FSL with baseline measures of cannabis use behavior and cannabis problems included as regressors to assess correlations between BOLD response and behavior change for youth problem cannabis use at each follow-up time point.

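### The H2 regressions and the H3 B path name only baseline use measures as covariates; age, sex, randomised arm and residual head motion are not named, so the brain-behaviour association is open to confounding.

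*Combined protocol and SAP*

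**What the plan says.** - **Group model.** Under Analysis Plan in section 8, H2a is tested by linear regression in FSL "with baseline measures of alcohol use behavior and alcohol problems included as regressors to assess correlations between BOLD response and behavior change", at each follow-up. H2b has the same form with baseline cannabis use and cannabis problems. H3 takes its A and B path coefficients from the H1 and H2 variables, so the B path has the same covariates.
- **Single-subject model.** One explanatory variable is named for each of the three statement types. Time series are motion corrected "using FSL's MCFLIRT module". No motion regressor, censoring rule, exclusion threshold or subject-level motion covariate is named.
- **Available but not named in any model.** The demographic questionnaire (section 6) records age and gender. On sleepiness, the plan says: "We will assess client sleepiness during the scan". Half the youth are randomised to MI and half to BAM, and the first intervention session precedes the scan.
- **Population.** Section 5b admits ages 14 to 19 and both sexes, with binge drinking "defined as 3+ drinks per drinking occasion for girls, and 4+ drinks per drinking occasion for boys". The Background (section 3) says that the brain regions governing judgement and self-regulation are still maturing at these ages.

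**The concern.** Participants are randomised to an intervention, not to a level of brain response. H2 and the B path are therefore observational, even though they sit inside a randomised trial. Any factor that shifts the BOLD contrast and also predicts later use, beyond the baseline use measures, will produce an association that is not an effect of brain response. The B path would pass that into the product-of-coefficients test as apparent mediation.

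Two candidates follow from the design itself. Age is one, because the Background gives developmental reasons to expect brain response to vary over this age range. Arm is the other, because it is assigned before the scan and could affect both the scan response and drinking.

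The stakes are practical. The Background says that a finding of mediation would be used to decide which treatment mechanisms to strengthen and to revise the MI manual. That is a causal use of the result.

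**Working it through.** **1. The plan's own figures.** The inputs, from Power Analysis and The Impact of Attrition in section 8, are: "Sample size was selected to evaluate the primary research questions at a two-tailed alpha of .05 and power of .80"; d = .70 for distal H2; "Together, this suggests the need for 68 youth to detect both proximal and distal behavior change for Hypothesis 2"; "we would need a sample of $N = 204$ to detect a mediated effect for Hypothesis 3"; and 16% attrition.
- A two-group t-test with d = .70, two-sided alpha .05 and power .80 needs 34 per group, 68 in total (power .812). This matches the plan.
- 204 / (1 − .16) = 242.9, rounded up to 243. This matches the plan. The 204 itself comes from a cited table and was not checked.
- H2 is a regression, so d is converted: r = d / √(d² + 4) = .70 / √4.49 = .330. The required N on that scale is 67, so the change of method does not alter the sample size.

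**2. Bias from one omitted factor.** Let C have correlation a with the BOLD contrast and b with the outcome, both after baseline adjustment, and let BOLD have no causal effect. The induced correlation is r = a·b. The rejection probability at N = 204 follows from Fisher's z, with mean atanh(r)·√(204 − 3) and critical values ±1.96. The documents give neither a nor b, so the values below are assumptions.

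| a = b (assumed) | induced r | rejection at N = 204 |
|---|---|---|
| .1 | .01 | 5% |
| .2 | .04 | 9% |
| .3 | .09 | 25% |
| .4 | .16 | 63% |

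Worked line for .4: atanh(.16)·√201 = .1614 × 14.18 = 2.29; Φ(2.29 − 1.96) = Φ(.33) ≈ .63. A noncentral F calculation with the two baseline covariates gives 5%, 9%, 25% and 64%.

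**3. What it takes to matter.** With two baseline covariates, significance at N = 204 needs r = .138. One factor's induced correlation reaches that at a = b = √.138 = .37. To produce the whole planned r = .330 from nothing, one factor needs √.330 = .57, and three independent factors need √(.330/3) = .33 each.

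**4. Several modest factors.** With three independent factors, induced r = 3a². Rejection at N = 204 is 7% for a = .1, 41% for .2 and 98% for .3. A simulation with 3,000 runs per setting gave 7.7%, 41% and 98% unadjusted, and 5.1%, 4.5% and 5.1% once the factors were in the model.

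**5. Cost of adjusting.** For one coefficient with k other covariates, f² = r²/(1 − r²) = .1225. The noncentrality is f²·N (8.33 at N = 68, 24.99 at N = 204), with 1 and N − k − 2 degrees of freedom. Going from the 2 baseline covariates to 6 (adding age, sex, arm and motion) moves power from .8113 to .8105 at N = 68 and leaves it at .9987 at N = 204. The required N stays 67.

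**The case against.** Several protections are already in the plan, and some stronger readings that a reader might infer are not supported.

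- **The association would be nothing but confounding.** This is possible in principle for any observational regression, but it is not shown here. At correlations of .1 the error rate barely moves, and a single factor would need .57 with both variables to mimic the planned effect.
- **Head motion is ignored.** It is not: realignment is planned and uses the motion estimates. The text names the statement-type regressors without saying that they are the only ones. What is missing is any stated handling of residual motion, and a motion summary would have to be derived, since it is not a listed variable.
- **The sex-specific binge threshold shows that sex confounds.** That threshold is quoted from an eligibility criterion. Baseline use and problems are adjusted for, which absorbs much of any stable difference by sex or age in drinking level. Nothing in the documents shows that sex or age strongly predicts the remaining change.
- **Within-person contrast.** The BOLD measure is a difference between statement types heard in the same run of about 13 minutes. General sleepiness, or motion unrelated to statement type, should largely cancel. This makes the upper correlations in the table less plausible. It does not protect against factors that change the contrast itself, as age or arm could.
- **Meaning of the rejection rates.** H2 is worded as an association. If an omitted factor induces r = .09, an association does exist, so the table describes error under a causal null. That bears on the B path and on any causal reading of H2, but not on H2 read strictly as correlation.
- **Simplification.** The table treats BOLD as one scalar tested at .05, and takes N = 204 from H3. The actual regressions run in FSL, and no scalar .05 test is stated for H2.

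**Conclusion.** The point holds as a gap in a stated model. H2a, H2b and the B path name only baseline use and problem measures, while age, sex, arm and residual motion are left out of a non-randomised comparison. The resulting association and mediated effect are open to confounding of unknown size. Under the stated assumptions (one omitted factor, equal correlations, no causal effect, one scalar test at N = 204), the nominal 5% rate becomes about 5%, 9%, 25% or 63% as the correlation goes from .1 to .4. The within-person contrast, baseline adjustment and realignment favour the lower part of that range but do not close the gap. The documents do not support a claim that the result would be spurious, and the planned sample size is unaffected. The change is worth making because it is cheap and because covariates fixed in advance cannot be chosen after the results are seen.

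**What to change.** - In H2a, H2b and the B path of H3, add age, sex, randomised arm and a per-participant mean-motion summary derived from the MCFLIRT output as fixed covariates, alongside the baseline measures already named.
- Add the six realignment parameters as nuisance regressors in each single-subject model.
- Prespecify a sensitivity analysis that adds the scan sleepiness rating.
- Report H2 results as associations, and state for H3 that the B path assumes no unmeasured confounding of brain response and outcome.

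This needs wording in section 8 only, with no new data or participants. The price is four degrees of freedom at group level, six nuisance regressors per scan, and a change in H2 power from .8113 to .8105 at N = 68, with none visible at N = 204.

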sample of eligible youth. Thus, we anticipate screening/enrolling a potential **500 youth** to generate the 243 youth who complete research procedures.

b) Inclusion and Exclusion Criteria

Participants. We anticipate screening 500 unique binge drinking youth. The approach for this study follows [name] prior NIH-funded work with the target population and is purposefully broad to maximize generalizability of study outcomes. Following our successful prior work in recruiting from community samples of substance-users, we will recruit adolescent binge drinkers via community based general media outlets (e.g., print, radio, internet) in the greater Portland metropolitan area. Examples of community based recruitment include advertising the study participation opportunity on undergraduate college and university "human subjects pool" websites (e.g., the University of Portland's SONA system), speaking with high school and college classes about the brain and related research participation opportunities, and recruiting at the OMSI Brain Fair.

We will also recruit adolescent binge drinkers through local juvenile justice departments (e.g., the Multnomah County Department of Community Justice (DCJ), Washington County Juvenile Department). These community-based youth may or may not be on probation and/or receiving services (e.g., family counseling). However, none of them will be incarcerated, detained, or otherwise mandated to reside in a residential facility. Individuals in a mandated residential setting, on parole, and/or participating in an electronic monitoring program (e.g., wearing an ankle bracelet) will not be eligible to participate. If any of the participants from community or justice department recruitment become incarcerated, on parole, or part of an electronic monitoring program during the duration of the study, then their participation in the study will be discontinued. We will recruit from the justice departments by disseminating information about study participation opportunities through flyers and brochures, which may in turn be disseminated by justice department staff. The justice departments will also provide sign-up sheets to youth who express interest in study participation to our research group, at which point we will follow up with interested youth as detailed below.

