To test **Hypothesis 3a** (from original submission) and 3 b (from supplement) that BOLD response (MFG, IFG, insula) will mediate the relationship between therapist behaviors (MI-consistent) and proximal and distal reductions in youth problem substance use (drinking; cannabis use), we will use the product of coefficients method (Sobel 1982). Because the distribution of the product of coefficients is typically not normal, we will apply appropriate asymptotic confidence limits (MacKinnon et al 2007) following Co-I [name]'s prior work examining causal chains in MI (Moyers et al 2009). Coefficients and standard errors for the A and B paths will be computed in FSL using the variables from Hypotheses 1 and 2 (i.e. signal change difference between MI-consistent and MI-inconsistent language, with (a) past month binge drinking/alcohol-related problems at 3-, 6- and 12-months; (b) past month cannabis use/cannabis-related problems at 3-, 6- and 12- months), and tested using the PRODCLIN macro (MacKinnon et al 2007). We will perform separate tests for proximal and distal drinking, each tested at $\alpha = .05$.

9) Privacy, Confidentiality and Data Security

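### The 12-month BOLD–drinking test uses only youth seen at 12 months, so loss tied to 3- or 6-month drinking would bias its slope, modestly at the projected 16% loss

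*Combined protocol and SAP*

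**What the plan says.** - **Section 8, Analysis Plan, Hypothesis 2a.** Linear regressions in FSL relate BOLD response to "behavior change for youth problem drinking at each follow-up time point". The only stated covariates are baseline alcohol use and baseline alcohol problems. Hypothesis 2b repeats the scheme for cannabis.
- **Section 8, Hypothesis 3.** The A and B paths come from the Hypothesis 1 and 2 variables and are tested as a product of coefficients: "We will perform separate tests for proximal and distal drinking".
- **Section 8, The Impact of Attrition.** The prior record is "retaining ~84% of adolescents at our most distal (12 month) follow-up", so "we project losing 16% of the proposed sample". Loss enters the plan only as this inflation of the sample size.
- **Section 5b.** For youth who become incarcerated, go on parole or enter electronic monitoring, "then their participation in the study will be discontinued".
- **Section 6, Follow-Up Procedures.** Remote measures are offered to limit missing data. This concerns conduct, not analysis.

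No longitudinal model, imputation method, missing-data assumption or sensitivity analysis appears. Dropping youth who miss a visit is the consequence of the chosen regressions, not a written rule.

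**The concern.** A regression of 12-month drinking can include only youth with a 12-month outcome. Many of those lost will have given 3- or 6-month drinking data, which this test does not use. Adjustment for baseline covers loss that depends on baseline drinking. It does not cover loss that depends on what happened afterwards, and discontinuation on a justice event is a post-baseline event plausibly tied to post-baseline drinking. The inflation to 243 protects the number of completers but does nothing about bias.

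The 12-month link is what the power section describes as not previously examined, and it also supplies the distal B path of Hypothesis 3. At stake is the accuracy of that slope and of its confidence interval.

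**Working it through.** **1. The plan's own figure.** Hypothesis 3 needs 204 youth and 16% are expected to be lost: 204 / (1 − 0.16) = 242.86, rounded up to 243. This reproduces the plan, and 243 × 0.84 = 204 youth remain at 12 months. (Section 5a speaks of 243 youth completing all procedures. I follow the attrition paragraph, whose arithmetic yields the figure.)

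**2. Effect size.** The distal effect is d = .70. Then r = d / √(d² + 4) = .70 / √4.49 = .330, so the standardized slope is -.330 (greater BOLD, less drinking).

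**3. When the planned slope is biased.** Write Y12 = a + b·BOLD + c·baseline + e12, fitted to youth seen at 12 months.
- If loss depends only on baseline, the retained e12 is unrelated to BOLD and b is unbiased.
- If loss depends on Y3 or Y6, the residuals are correlated across visits, and BOLD affects Y3 or Y6, then the mean of e12 among retained youth varies with BOLD and b is biased.
- If BOLD is unrelated to drinking at every visit, there is no bias.

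**4. Size, by simulation.** These inputs are assumptions, not in the documents: normal standardized index, baseline coefficient .5, residual correlation between visits .5 to .7, odds ratio of loss 2 or 4 per SD, complete 3- and 6-month data, and drinking as the response. Loss is 16%. The comparator is the maximum-likelihood estimate from all visits with unstructured covariance and visit-specific slopes. Large-sample results (random and baseline rows at correlation .5; other ranges run from .5 to .7):

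| Loss depends on | Odds ratio | Planned slope | Shrinkage | Likelihood slope |
|---|---|---|---|---|
| Nothing (random) | 1 | -.331 | none | -.331 |
| Baseline | 2; 4 | -.331; -.330 | none | -.331; -.330 |
| 6-month drinking | 2 | -.324 to -.322 | 2.0–2.5% | -.330 |
| 6-month drinking | 4 | -.314 to -.306 | 5.0–7.3% | -.330 to -.329 |
| 3- and 6-month drinking | 2 | -.324 to -.321 | 2.0–2.9% | -.331 to -.330 |
| 3- and 6-month drinking | 4 | -.309 to -.304 | 6.6–7.9% | -.329 to -.330 |
| Unseen 12-month drinking | 2 | -.317 to -.319 | 3.9–3.5% | -.321 to -.325 |
| Unseen 12-month drinking | 4 | -.297 | 10.2–10.0% | -.307 to -.316 |

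**5. At N = 243, loss on 6-month drinking.** The standard error of the planned slope is about .056.
- Odds ratio 2: mean slope -.325 (correlation .5) or -.322 (.7). The bias is .005 / .056 = 0.09 or .008 / .056 = 0.14 standard errors. Coverage of the 95% interval is 94.7% or 94.0%.
- Odds ratio 4, correlation .7: mean slope -.305. The bias is .025 / .056 = 0.45 standard errors and coverage is 92.0%. Root mean square error is .062, against .055 for the likelihood model.
- Power at d = .70 stays near 100% in each case.

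Allowing for simulation error and for which earlier visit drives loss, I take coverage as about 91–95%.

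**6. BOLD acting at 3 and 6 months but not at 12** (correlation .7, loss on 6-month drinking). The planned regression gives a false 12-month slope of .008 (odds ratio 2) or .022 (odds ratio 4), with type I error of 5.0% or 6.6%. The likelihood estimate stays within .002 of zero. The false slope is positive, so in these runs it does not imitate the hypothesized benefit.

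**The case against.** Several stronger readings are tempting, and the documents do not support them.

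- *Any loss linked to earlier drinking biases the slope.* Baseline drinking is earlier drinking and is already a regressor; loss driven by it gave no bias.
- *The shrinkage is 10% or more.* With loss on observed 3- and 6-month drinking, about 9–12% needs odds of loss rising 7.4-fold per SD. With 16% lost overall, the heaviest tenth of drinkers would then lose about 68% and the lightest tenth about 0.3%. The documents give only an overall retention figure and no link between drinking and loss.
- *The distal test loses its power.* It does not. Under random or baseline-driven loss the longitudinal model lowers the standard error only from .056 to .055.
- *A longitudinal model removes the problem.* It does so only for loss that depends on observed data. For loss on unseen 12-month drinking it remained 1.5–7.0% shrunk in the table above, and up to 8.8% at correlation .3. A justice event may follow drinking after the last completed visit. Youth with no follow-up add nothing to either analysis.

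The direction of the regression is also open. In a voxelwise FSL model BOLD would be the response and drinking a regressor. The shrinkage is then about half or less: 1.6–2.2% against 3.8–5.0% at a 2.7-fold odds ratio.

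Finally, testing 3 and 6 months separately is a legitimate question about when change occurs. Averaging them is a preference, not a correction.

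These objections limit the size of the problem. They do not supply a missing-data assumption, and in the settings tried the planned regression never did better than the likelihood model.

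**Conclusion.** The point holds in a limited form. The planned 12-month test discards observed 3- and 6-month drinking. Its slope is biased if loss depends on that drinking beyond baseline and BOLD is related to it. At 16% loss, with assumed odds ratios of 2–4 per SD and visit correlations of .5–.7, the shrinkage is about 2–8% of a slope of -.33. That is well under one standard error, with coverage of about 91–95% and power essentially unchanged. If BOLD acts early but not at 12 months, a false slope of about .02 can appear at the upper end of this range. The loss mechanism and the correlations are assumptions; the 16%, the effect size and the separate regressions are the plan's. This should be fixed because the remedy is cheap. It does not show that the planned conclusions would be wrong.

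**What to change.** For the Hypothesis 2 tests and the Hypothesis 3 B path:

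1. Extract each youth's mean contrast in predefined MFG, IFG and insula masks. The hypotheses are posed in these regions, and the product-of-coefficients test already needs one coefficient per path.
2. Fit one repeated-measures likelihood model per outcome, with visit, BOLD × visit, baseline drinking × visit, arm and unstructured covariance. Report the 3-, 6- and 12-month slopes from it. The visit-specific terms matter, since a common slope would blend the visits. An average of the 3- and 6-month slopes is optional.
3. Alternatively, keep the planned regressions and multiply impute 12-month drinking using 3- and 6-month drinking.
4. State the missing-data assumption. Add a sensitivity analysis for loss that depends on unseen 12-month drinking, including discontinuation on incarceration, parole or monitoring.
5. Keep the whole-brain FSL maps as planned.

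The cost is SAP text, mask definitions fixed in advance, and standard mixed-model or imputation code. Under option 2 the region-level test, including the B-path coefficient, runs outside FSL. No extra youth, visits or data are needed.
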